6.7.1 Treatment Guidelines for QTc Prolongation

Immediate medical management of patients will be based on the following:

- 1. Baseline: A pre-infusion (baseline) ECG will be obtained on all patients, if the automated measurements indicate a QTcF of \geq 450 msec
 - a. The single QTcF will be verified by manually measuring at least 3 complexes within the ECG and determining the average QTcF
 - b. All patients must have a pre-infusion QTcF of < 450 msec by either:
 - i. Calculation using the automated measurements of the first ECG or
 - ii. The manual measurement of a single ECG

If it is determined that the manually read QTcF \geq 450 msec, the Medical Monitor should be contacted to discuss the clinical significance of the reading and to determine if it is appropriate to move forward with the infusion.

2. During treatment: Grade 3 QTc prolongation (any QTcF that is ≥ 501 msec OR > 60 msec QTcF increase relative to pre-infusion) will be manually verified by measuring at least 3 complexes with the ECG and determining the average QTcF. If QTcF prolongation is ≥ Grade 3, an ECG may need to be repeated more frequently during a patient's visit, depending on the degree of the prolongation, as indicated in Table 7 and per institutional standards.

Note: Dose modification will be based on the average QTcF using the manual measurements.

Confidential and Proprietary

If the Investigator has any question regarding the local automated reading, a local cardiologist should be consulted. Treatment guidelines for patients experiencing QTc prolongations are provided in (Table 7).

Patients who experience \geq Grade 3 QTc prolongation must be assessed by the Investigator (or qualified designee) prior to discharge.

Table 7: Treatment Guidelines for QTc Prolongation

QTc Prolongation	After Tarloxotinib Administration		
Grade 1 450 to 480 msec QTcF	 Cycle 1 and Cycle 2 Day 1 May be discharged if the 4-hour (or later) post-infusion QTcF is Grade 1 or lower and asymptomatic After Cycle 2 Day 1 Obtain pre-infusion and 2-hour post-infusion ECGs May be discharged if the 2-hour (or later) post-infusion QTcF is ≤ Grade 1 and the patient is asymptomatic 		

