8.5 Reporting QTc Prolongation

QT prolongation is not unexpected but it is an AE of special interest (AESI). Grade 3 AESIs require expedited reporting to the Sponsor. ECGs will be obtained throughout the study and will be read locally at the investigational sites. Grade 3 QTc prolongation (absolute QTcF of \geq 501 msec or QTcF increase of > 60 msec relative to pre-infusion) or Grade 4 QTc prolongation will be reported as an AESI.

Any apparent Grade 3 AESIs should be verified by manually measuring at least 3 complexes within the ECG and determining the average QTcF.

AESIs will be reported by submitting an AESI Report to:

[contact]

All events of Grade 3 QTc prolongation (absolute QTcF of \geq 501 msec or QTcF increase of \geq 60 msec relative to pre-infusion) or Grade 4 QTc prolongation will be reported as an AESI unless the event met the criteria of serious (see Section 8.1.1.4) in which case it will be reported as an SAE.

Confidential and Proprietary

Table 12: NCI CTCAE Grading of ECG QTc Prolongation (Medical Dictionary of Regulatory Activities Code: 10014383)

ECG QTc Prolongation NCI CTCAE Grade					
1	2	3	4	5	
Average QTc	Average QTc	Average	Torsade de Pointes	Not applicable	
450 to 480 msec	481 to 500 msec	$QTc \ge 501 \text{ msec}$	OR		
		OR	polymorphic		
		> 60 msec change	ventricular		
		from baseline*	tachycardia		
			OR		
			signs/symptoms of		
			serious arrhythmia		

Adapted from NCI CTCAE v5.0

ECG = electrocardiogram; NCI CTCAE = National Cancer Institute Common Terminology Criteria for Adverse Events; QTc = corrected QT interval; QTcF = corrected QTc interval as calculated according to Fridericia's formula

Definition of QTc prolongation: A finding of a cardiac dysrhythmia characterized by an abnormally long QTc * Although a Grade 3 event (≥ 501 msec OR > 60 msec change from baseline) is reportable as an adverse event of special interest, dose reductions are not required for patients with absolute QTcF ≤ 500 msec and a ≤ 60 msec QTcF change from baseline.

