#### 9.2.8 Baseline Values

Baseline values are defined as the last, non-missing assessment prior to the first dose of study drug.

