#### 14.4 12-Lead Electrocardiogram

Electrocardiogram (ECG) data, such as clinical interpretation of ECGs, heart rate (HR) values, and interval assessments of QRS duration, PR interval, QT interval, and the Fridericia's corrected value of the interval between the Q and T waves on the ECG tracing (QTcF) will be listed. Descriptive statistics for observed values and change from baseline at each scheduled time point will be presented for these 12-lead ECG interval and HR assessments will be presented as actual values and as changes from the baseline values by 6-point descriptive summary statistics (n, mean, SD, median, minimum, and maximum). The numbers and percentages of subjects who meet categorical analyses such as the following criteria at each scheduled ECG time point will be presented.

- Absolute QTcF interval:
  - o QTcF interval < 450
  - o QTcF interval 451 to 480 msec
  - o QTcF interval 481 to 500 msec
  - o QTcF interval  $\geq$  501 msec
- Change from predose baseline in QTcF interval:
  - $\circ \le 30 \text{ msec}$
  - o 31 to 60 msec
  - o 60 msec

The numbers and percentages of subjects meeting each criterion will be summarized for each ECG time point, as well as for each subject overall at any time.

Abnormal ECG findings not present at the pre-dose baseline will be summarized as the number of subjects with each finding at 1 or more ECG times. Descriptive waveform morphology changes will be provided.

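### The SAP's QTcF categories omit 450 msec, which the protocol grades as Grade 1, and measure change from a different ECG than the protocol's Grade 3 criterion (minor)

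*SAP*

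**What the plan says.** SAP 14.4 counts subjects by category at each scheduled ECG time and at any time. The absolute categories are "QTcF interval < 450", "QTcF interval 451 to 480 msec", "QTcF interval 481 to 500 msec" and a top category from 501 msec upward. Change is tabulated under the label "Change from predose baseline in QTcF interval", with cuts at 30 and 60 msec. The last change line is printed without a sign. Protocol 9.7.1 has a greater-than sign there, so I read it that way and do not count it as an error.

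Section 14.4 does not say which ECG is the predose baseline. The SAP's only definition of baseline is in 9.2.8: "Baseline values are defined as the last, non-missing assessment prior to the first dose of study drug".

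In the protocol, Table 7 (section 6.7.1) has "Grade 1 450 to 480 msec QTcF", then Grade 2 from 481 to 500 msec, and Grade 3 from 501 msec or on a rise above 60 msec. Table 12 (section 8.5) uses the same limits. For the rise, 8.5 has "QTcF increase of > 60 msec relative to pre-infusion", and 6.7.1 and 6.9.2.1 use the same reference. Protocol 9.7.1 already contains the SAP's absolute categories and its label for change.

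**The concern.** Protocol 2.5 names QT prolongation as the main identified risk. In the two earlier Phase 2 studies (protocol 2.3.2), 16 patients (34%) had a change above 60 msec and 10 (21%) reached 501 msec or more. In TH-CR-601 the Grade 3 events came mainly from the change criterion (38%, against 10% by absolute value). The choice of reference ECG therefore bears on the criterion that produced most of the Grade 3 events in that study.

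The value 450 is not arbitrary either. It is the entry limit (protocol 5.1), the pre-infusion limit (6.5) and the trigger for manual verification (6.7.1).

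The SAP drops the analysis of exposure against cardiac repolarization (5.1.2) and keeps the ECG analysis descriptive, so readers will lean on this table. Where it disagrees with a subject's grade, the summary alone will not show the reason.

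**Working it through.** The plan states no figure to reproduce here. The check applies the written limits to possible values.

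**1. Absolute scale, whole msec.** I classified every integer from 400 to 600 by the SAP 14.4 categories and by the limits in protocol Tables 7 and 12.

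- No SAP category: 450 only.
- No protocol grade or normal range: none. The value 450 is Grade 1.
- If the lowest category were meant to include 450, that value would be counted below Grade 1 and would still disagree with both tables.

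**2. Absolute scale, averages.** Protocol 6.7.1 and 8.5 call for averaging at least 3 complexes when a reading is verified. I found no rounding rule in either document. Assuming 3 complexes, each read in whole msec, averages move in steps of 1/3 msec. From 440 to 510 there are 70 × 2 = 140 non-integer averages.

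| Average (msec) | SAP category | Protocol grade |
|---|---|---|
| 450.33, 450.67 | none | 1 |
| 480.33, 480.67 | none | none |
| 500.33, 500.67 | none | none |

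So 6 of the 140 have no SAP category, and 4 of those 6 have no protocol grade either. The stretch that is graded but has no category runs from 450 to just under 451 msec.

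**3. Change scale.** SAP 14.4 has 30 or less, 31 to 60, and above 60. Every whole number is placed; only values strictly between 30 and 31 are not.

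**4. Reference for change.** Let B be the last QTcF before the first dose (SAP 9.2.8), P the pre-infusion QTcF at a later infusion, and X a QTcF after that infusion. The SAP change is X − B. The protocol's Grade 3 change is X − P. They differ by (X − B) − (X − P) = P − B. The values below are invented for illustration. All have P below 450 and X below 501, so only the change component can make Grade 3.

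| B | P | X | SAP: X − B | Protocol: X − P |
|---|---|---|---|---|
| 430 | 400 | 465 | +35, not above 60 | +65, above 60 |
| 400 | 430 | 470 | +70, above 60 | +40, not above 60 |

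At Cycle 1 Day 1, P = B if the pre-infusion ECG is the last one before dosing, and the two agree. They can part from the second infusion on, in either direction.

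**5. Weight of one subject.** SAP Table 1 gives 41 enrolled: 11 in Cohort A, 22 in B and 8 in C. If all have ECG data, one reclassified subject moves the overall percentage by 1/41 = 2.4 points, and the cohort percentage by 1/11 = 9.1, 1/22 = 4.5 or 1/8 = 12.5 points.

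**The case against.** The case against giving this much weight is substantial.

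- **Inheritance.** The 450 gap and the label for change come from protocol 9.7.1, and the SAP introduces its list with "categorical analyses such as the following criteria at each scheduled ECG time point will be presented", so the list is illustrative. Both facts are right. Neither gives 450 msec a category.
- **Rounding.** Every limit is in whole msec, automated readings are the default (protocol 8.7), and nothing says that averages are stored unrounded. This stands: the non-integer gaps are conditional, and with whole-msec data only 450 is lost.
- **Grading happens elsewhere.** Section 14.4 does not claim to grade events. Adverse events are graded by CTCAE v5.0 (SAP 9.2.18), and Grade 3 or higher events are tabulated (14.1.2, 14.1.3). This stands, so grades are not lost from the report.
- **Baseline wording.** The protocol itself labels the pre-infusion ECG as baseline in 6.7.1, and words the rise as change from baseline after Table 7 and in Table 12. A summary against the first-dose value also answers a legitimate question of its own. This stands in part. The terms are ambiguous, but SAP 9.2.8 is explicit and SAP section 4 makes the SAP govern.

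A reader might infer more than the documents support:

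- That category counts should add up to the number of ECGs. The table counts subjects.
- That the count above 60 msec should equal the Grade 3 count of adverse events of special interest. That event is a composite of 501 msec or more or the rise; Grade 4 is reported in the same class, and serious cases go to serious-event reporting instead. Section 8.5 also states the rise in two ways, above 60 and at least 60 msec. The counts would differ under any baseline.
- That a mismatch could not be traced. SAP 14.4 lists the individual QTcF values.
- That the SAP fails to match the protocol's grades throughout. Only 450 to just under 451 msec is graded but has no category.

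**Conclusion.** Two narrow points hold. First, a QTcF of exactly 450 msec is Grade 1 in the protocol and has no category in SAP 14.4 or protocol 9.7.1. This needs no assumption. The further openings, at 450–451, 480–481 and 500–501 msec and at changes of 30–31 msec, exist only if unrounded averages are analysed. Second, reading 14.4 with 9.2.8, the change categories use the value before the first dose, whereas the protocol's criterion uses each infusion's pre-infusion ECG. From the second infusion on, a subject's category above 60 msec can disagree with the change component of Grade 3 in either direction.

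The size cannot be given. The documents do not report how many values fall in the gaps or how far pre-infusion QTcF drifts from the first-dose baseline. The 34% and 21% from the earlier studies show that the upper categories matter, but they do not measure the discrepancy. With a descriptive table for 41 subjects, individual values listed and events graded separately, the severity is minor.

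**What to change.** Change the analysis text only:

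- In SAP 14.4, start the second absolute category at 450 msec, and record in SAP section 15 that this departs from protocol 9.7.1.
- State that QTcF is rounded to whole msec before categories, grades and changes are derived. All values then have a place and the categories line up with the grade limits. Contiguous limits (below 450, 450 to 480, above 480 to 500, above 500) would also close the gaps, but would put 500.33 in the top category while the protocol's Grade 3 starts at 501. Rounding is the cleaner choice.
- Define the predose baseline in 14.4, and tabulate the change categories twice: against the first-dose baseline and against the same-day pre-infusion ECG.
- Reconcile the two wordings of the 60 msec limit in protocol 8.5, and state which one the reported events followed.

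The cost is a few lines of SAP text and one extra block of columns. Pre-infusion ECGs were scheduled at every infusion, so no new data are needed, and no dosing or monitoring rule changes.

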#### 15 CHANGES RELATIVE TO THE PROTOCOL-SPECIFIED ANALYSIS

Protocol Section 9.2.3 states "Deviations will be defined prior to database lock. Handling of major deviations in statistical analyses will be defined in the SAP" and further defines a Per-Protocol analysis set excludes subjects with certain, pre-specified deviations. RAIN-701 was terminated and the analysis will support an abbreviated clinical study report, which does not include protocol deviations per FDA guidance for industry, Submission of Abbreviated Reports and Synopses in Support of Marketing Applications. Analysis will be performed on the safety population which includes all subjects who received at least 1 dose of tarloxotinib. Analysis of a Per Protocol (PP) population where subjects with major protocol deviations are removed is not necessary for the aCSR. The abbreviated CSR will provide a comprehensive safety analysis for all subjects receiving at least 1 dose of tarloxotinib. Additionally, the primary efficacy analysis of ORR will include all treated subjects. Efficacy analyses are not interpretable as RAIN-701 was terminated and did not enroll the intended sample size to support statistical analyses.

Protocol Section 7 states, "In accordance with RECIST v1.1, response (PR and CR) must be confirmed by a second tumor assessment at least 8 weeks after the initial observed response." SAP Section 6.3.1 text instead states that the confirmation assessment must be at least 4 weeks after the initial observed response, which is aligned with the true RECIST v1.1 criteria. The efficacy endpoint (Section 9.2.13) still follows the protocol text in defining the disease control for at least 8 weeks (2 cycles).

Protocol Table 12 states "Microscopic sediment evaluation, as clinically indicated" as a urinalysis assessment, but these microscopic sediment urinalysis assessments were not collected. Similarly, Protocol Table 12 lists ALP as a serum chemistry assessment, but it was not collected.

Units and reference ranges of the local laboratory assessments were not collected. The Sponsor has assigned units and lab normal ranges for each parameter (e.g., lower limit of normal, upper limit of normal) based on available information and Harrison's Principles of Internal Medicine (Appendix A).

Rain Therapeutics Inc. RAIN-701 SAP

Version 1.0, 14 October 2022

Adverse events were coded with MedDRA version 22.0 and medical history events were coded with MedDRA version 23.0.

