#### 14.2 Clinical Laboratory Evaluation

Results for clinical laboratory parameters (serum chemistry and hematology), vital signs, ECGs, and physical examinations will be summarized by cohort and combined and by study visits.

Descriptive summary statistics in observed values as well as changes from baseline will be

presented. In addition, thresholds of marked laboratory abnormalities based on NCI CTCAE v5.0 will be summarized by worst grade shift from baseline (see Appendix B).

Table 7 shows clinical laboratory assessments (hematology, chemistry, and urinalysis) that were performed performed. Chemistry and hematology laboratory parameters will be summarized by cohort and scheduled visit. Urinalysis assessments will be listed but not summarized due to their qualitative nature.

**Table 7** Clinical Laboratory Parameters

Chem	istry	Hematology	Urinalysis
Sodium	Creatinine	Hematocrit	Specific gravity
Potassium	Total Bilirubin	Hemoglobin	Protein
Chloride	AST/SGOT	WBC count	Glucose
Bicarbonate	ALT/SGPT	Neutrophils	Ketones
Calcium	<del>ALP</del> ‡	Lymphocytes	Urobilinogen
Magnesium	Albumin	Monocytes	Occult blood
Phosphorous	Total protein	Eosinophils	Microscopic sediment
			evaluation ‡
Glucose		Basophils	
Blood urea nitrogen		Platelet count	WOCBP only:
			β-HCG§

ALT = alanine aminotransferase; ALP = alkaline phosphatase; AST = aspartate aminotransferase; HCG = β-human chorionic gonadotropin pregnancy; SGOT = serum glutamic-oxaloacetic transaminase; SGPT = serum glutamic pyruvic transaminase; WBC = white blood count; WOCBP = women of child-bearing potential

Numeric results will be summarized using (6-point) descriptive statistics at baseline and at each scheduled post-baseline time point, unless otherwise specified. Changes from baseline will also be summarized by scheduled time point, where available. Selected laboratory results will be listed with CTCAE reference ranges.

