### 17 Appendix A: Local Laboratory Units and Reference Ranges by Site and Parameter When a reference range is followed by an asterisk, it is sourced from Harrison's Principles of Internal Medicine, 19th edition.

 Table 8
 Site 101 Units and Reference Ranges by Parameter

SITE NUMBER	PANEL	PARAMETER	SEX	AGE	UNITS	REFERENCE LOW	REFERENCE HIGH
101	Chemistry	Albumin			g/dL	3.5	5
101	Chemistry	ALP			/L	45	117
101	Chemistry	ALT/SGPT			/L	15	41
101	Chemistry	AST/SGOT			/L	3	34
101	Chemistry	Bicarbonate			mmol/L	18	23
101	Chemistry	Blood urea nitrogen	M		mg/dL	9	20
101	Chemistry	Blood urea nitrogen	F		mg/dL	7	17
101	Chemistry	Calcium			mmol/L	1.12	1.32
101	Chemistry	Chloride			mmol/L	98	107
101	Chemistry	Creatinine	M		mg/dL	0.66	1.5
101	Chemistry	Creatinine	F		mg/dL	0.52	1.04
101	Chemistry	Glucose			mg/dL	65	140
101	Chemistry	Magnesium			mg/dL	1.6	2.3
101	Chemistry	Phosphorous			mg/dL	2.5	4.5
101	Chemistry	Potassium			mmol/L	3.5	5.1
101	Chemistry	Sodium			mmol/L	137	145
101	Chemistry	Total Bilirubin			mg/dL	0.2	1.3
101	Chemistry	Total protein			g/dL	6.3	8.2
101	Hematology	Basophils			k/uL	0	0.2
101	Hematology	Eosinophils			k/uL	0	0.7
101	Hematology	Hematocrit	M		%	37.5	49.5
101	Hematology	Hematocrit	F		%	34.5	44
101	Hematology	Hemoglobin	M		g/dL	12.5	16.5
101	Hematology	Hemoglobin	F		g/dL	11	14.5
101	Hematology	Lymphocytes			k/uL	0.6	4.9
101	Hematology	Monocytes			k/uL	0.1	1.3
101	Hematology	Neutrophils			k/uL	1.7	8.1
101	Hematology	Platelet count			k/uL	145	400

SITE NUMBER	PANEL	PARAMETER	SEX	AGE	UNITS	REFERENCE LOW	REFERENCE HIGH
101	Hematology	WBC count			k/uL	4	10.8
101	Urinalysis	Glucose				Normal	
101	Urinalysis	Ketones				Negative	
101	Urinalysis	Occult blood				Negative	
101	Urinalysis	Protein				Negative	
101	Urinalysis	Specific gravity				1.003	1.03
101	Urinalysis	Urobilinogen			mg/dL	< 2.0	
Table 9	Site 102 Uni	ts and Reference	Range	s by P	arameter		
SITE			C			REFERENCE	REFERENCE
NUMBER 102	PANEL	PARAMETER Albumin	SEX	K AGI		LOW 3.5*	HIGH 5.5*
	Chemistry Chemistry	ALP			g/dL	3.3	3.3
102					T T /T	7*	41*
102	Chemistry	ALT/SGPT AST/SGOT			U/L		
102	Chemistry	AS1/SGO1 Bicarbonate			U/L	12*	38*
102	Chemistry				meq/L	22* 7*	30*
102	Chemistry	Blood urea nitrogen			mg/dL	·	20*
102	Chemistry	Calcium			mg/dL	8.7*	10.2*
102	Chemistry	Chloride	Б		meq/L	102*	109*
102	Chemistry	Creatinine	F		mg/dL	0.5*	0.9*
102	Chemistry	Creatinine	M		mg/dL	0.6*	1.2*
102	Chemistry	Glucose			mg/dL	65*	95*
102	Chemistry	Magnesium			mg/dL	1.5*	2.3*

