# 18 Appendix B: Common Terminology Criteria for Adverse Events for Laboratory Parameters

Table 20 Common Terminology Criteria for Adverse Events v5.0. November 27, 2017

Laur			Table 20 Common telliminology efficial for Adverse Events 43.6, 100 cm feet, 2017	LS V J.U9 LIUV VIIIR	107 6/7 10			
Panel	Parameter	CTCAE Term	Definition	Grade 1	Grade 2	Grade 3	Grade 4	Grade 5
Chemistry	Sodium	Hypernatremia	A disorder characterized by laboratory test results that indicate an elevation in the concentration of sodium in the blood.	>ULN - 150 mmol/L	>150 - 155 mmol/L; intervention initiated	>155 - 160 mmol/L; hospitalization indicated	>160 mmol/L; life-threatening consequences	Death
Chemistry	Sodium	Hyponatremia	A disorder characterized by laboratory test results that indicate a low concentration of sodium in the blood.	<pre><lln -="" 130="" l<="" mmol="" pre=""></lln></pre>	125-129 mmol/L and asymptomatic	125-129 mmol/L symptomatic; 120- 124 mmol/L regardless of symptoms	<120 mmol/L; life-threatening consequences	Death
Chemistry	Potassium	Hyperkalemia	A disorder characterized by laboratory test results that indicate an elevation in the concentration of potassium in the blood; associated with kidney failure or sometimes with the use of diuretic drugs	>ULN - 5.5 mmol/L	>5.5 - 6.0 mmol/L; intervention initiated	>6.0 - 7.0 mmol/L; hospitalization indicated	>7.0 mmol/L; life- threatening consequences	Death
Chemistry	Potassium	Hypokalemia	A disorder characterized by laboratory test results that indicate a low concentration of potassium in the blood.	<lln -="" 3.0
mmol/L</lln>	Symptomatic with <lln -="" 3.0="" indicated<="" intervention="" l;="" mmol="" th=""><3.0 - 2.5 mmoVL; hospitalization indicated	<2.5 mmol/L; life- threatening consequences	Death	</lln>	<3.0 - 2.5 mmoVL; hospitalization indicated	<2.5 mmol/L; life- threatening consequences	Death
Chemistry	Calcium	Hyper-calcemia	A disorder characterized by laboratory test results that indicate an elevation in the concentration of calcium (corrected for albumin) in blood.	>ULN - 2.9 mmol/L	>2.9 - 3.1 mmol/L; symptomatic	>3.1 - 3.4 mmol/L; hospitalization indicated	>3.4 mmol/L; life- threatening consequences	Death

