Chemistry	Calcium	Hypocalcemia	A disorder characterized by laboratory test results that indicate a low concentration of calcium (corrected for albumin) in the blood.	<lln -="" 2.0
mmol/L</lln>	<2.0 - 1.75 mmol/L; symptomatic	<pre><1.75 - 1.5 mmo//L; hospitalization indicated</pre>	<1.5 mmol/L; life- threatening consequences	Death

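### Calcium limits assigned at Sites 101 and 113 do not fit the albumin-corrected CTCAE table; analyte and unit need checking before calcium is graded or pooled

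*SAP*

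**What the plan says.** SAP Section 15 reports that units and reference ranges of the local laboratories were not collected, and continues: "The Sponsor has assigned units and lab normal ranges for each parameter". The stated basis is available information and a medical textbook. An asterisk in Appendix A marks the textbook rows.

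SAP 14.2 says that CTCAE v5.0 laboratory abnormalities "will be summarized by worst grade shift from baseline (see Appendix B"). It also plans observed values and changes from baseline by cohort and visit, and SAP 10.3 pools all centers.

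The Site 101 row reads "101 Chemistry Calcium mmol/L 1.12 1.32". The Site 113 row is 4.5 to 5.6 mg/dL. Neither carries an asterisk. For contrast, the textbook-sourced Site 102 row reads "102 Chemistry Calcium mg/dL 8.7* 10.2".

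For calcium, Appendix B has only albumin-corrected criteria; its hypocalcemia entry covers results "that indicate a low concentration of calcium (corrected for albumin) in the blood". The bounds used below are:
- hypocalcemia Grade 1, from below LLN down to 2.0 mmol/L; Grade 2 "<2.0 - 1.75 mmol/L; symptomatic"; Grade 3, below 1.75 down to 1.5 mmol/L; Grade 4 "<1.5 mmol/L; life- threatening consequences"
- hypercalcemia Grade 1 ">ULN - 2.9 mmol/L"; Grade 4, above 3.4 mmol/L

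The SAP gives no ionized-calcium criteria and no albumin-correction formula. It does not say whether a value must be below LLN before a hypocalcemia grade applies.

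**The concern.** The two assigned ranges and the grading table do not describe the same quantity. Grade 1 is anchored to the assigned LLN or ULN, while Grades 2-4 use fixed mmol/L bounds set for total, albumin-corrected calcium. An LLN of 1.12 mmol/L lies below every one of the fixed hypocalcemia bounds, so the ordering that the table needs (LLN above 2.0, above 1.75, above 1.5) fails.

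SAP Section 4 describes the purpose as a comprehensive safety analysis, with efficacy only summarized, so the safety tables are the main product. Calcium also has a role in the trial: Protocol 6.5 requires pre-infusion calcium to be normal unless an exception is approved. Most pre-infusion results should therefore have been locally normal, and a table showing them as abnormal at two sites would mislead.

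**Working it through.** **1. Put all ranges on one scale.** With a molar mass for calcium of 40.08 (an assumption from outside the documents), mmol/L = mg/dL x 10 / 40.08.

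- Site 101: 1.12-1.32 mmol/L as printed.
- Site 113: 4.5 x 10/40.08 = 1.12; 5.6 x 10/40.08 = 1.40 mmol/L.
- Site 102 (textbook): 8.7 gives 2.17; 10.2 gives 2.54 mmol/L.
- Other ten sites, all age rows: LLN from 2.05 (Site 122, over 90 years, 8.2 mg/dL) to 2.24 (Site 110, 59 and over); ULN from 2.40 (Site 122, over 90 years, 9.6 mg/dL) to 2.63 (Site 110, 59 and over).

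**2. Apply Appendix B.** Only the numeric cut points are used; qualifiers such as symptoms or hospitalization are ignored. Each cell shows hypocalcemia grade with fixed bounds alone / hypocalcemia grade if the value must also be below LLN / hypercalcemia grade.

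| Calcium (mmol/L) | Site 101 limits | Site 107 limits (2.2-2.62) |
|---|---|---|
| 1.10 | 4 / 4 / 0 | 4 / 4 / 0 |
| 1.20 | 4 / 0 / 0 | 4 / 4 / 0 |
| 1.6 | 3 / 0 / 1 | 3 / 3 / 0 |
| 1.9 | 2 / 0 / 1 | 2 / 2 / 0 |
| 2.05 | 0 / 0 / 1 | 1 / 1 / 0 |
| 2.35 | 0 / 0 / 1 | 0 / 0 / 0 |

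Site 113 limits give the same grades as Site 101 for all six values.

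**3. Read the result under each possibility.**

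- *Recorded values match the assigned limits.* Both ULNs (1.32 and 1.40) are below 1.5, so every in-range value is Grade 4 under the fixed bounds. Baselines are then already at the top grade and no worsening can appear. With a below-LLN check, in-range values are Grade 0, but any value below 1.12 is also below 1.5 and goes directly to Grade 4.
- *Recorded values are total calcium, unit known.* The whole interval 2.17-2.54 exceeds 1.32 and 1.40 and stays below 2.9, so all of it is Grade 1 hypercalcemia. Grade 1 hypocalcemia would have to lie below 1.12 and at or above 2.0, which is empty. Grades 2-4 keep their fixed bounds: 1.9 is still Grade 2 low and 1.6 still Grade 3 low, although both also pick up a spurious Grade 1 high. Only if a below-LLN check were added would those low grades disappear.

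**4. Pooled summaries.** Appendix A mixes mg/dL and mmol/L for calcium, so pooling across sites relies on the assigned units. As an illustration, if Sites 101 and 113 recorded ionized values near 1.20 and the rest total values near 2.35, a cohort mean would fall by (2.35 - 1.20) = 1.15 mmol/L times those sites' share of subjects. A unit error between mg/dL and mmol/L would change a value by a factor of 40.08/10, about 4.

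**5. Secondary: hemoglobin.** Sites 104 and 113 have one range for both sexes, with LLN 13.5 and 14.1 g/dL. Female LLNs at the ten sites with sex-specific ranges run from 11.0 to 12.1 g/dL. The excess is 13.5 - 12.1 = 1.4 to 13.5 - 11.0 = 2.5 g/dL at Site 104, and 14.1 - 12.1 = 2.0 to 14.1 - 11.0 = 3.1 g/dL at Site 113. Anemia Grade 2 and above has fixed bounds, so only Grades 0-1 in women are affected.

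**The case against.** The case for leaving this alone is reasonable. Section 15 discloses that limits were assigned. The report is abbreviated and descriptive, for a terminated study of 41 subjects. One analyte at two sites is involved, and no recorded value is visible to us. Values near 1.2, 2.35 or 9.4 are easy to tell apart on inspection, so a programmer may notice. Protocol 8.9 has clinically significant laboratory results reported as AEs. Appendix A belongs to a SAP written after database lock, so it could not have affected dosing.

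Most of this limits the consequence and stands. It does not remove the conflict. Section 15 says that ranges were assigned, not that two of them are incompatible with the grading table, and the SAP declares itself the governing text. AE reporting is a partial safeguard because it depends on the investigator's judgement of significance.

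A text-extraction fault is possible, since the Site 113 rows around calcium contain a stray character. But two sites in two different units give the same LLN, 1.12 mmol/L, which a stray digit would not produce.

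Some other readings are tempting but not supported:
- *Sites 101 and 113 report ionized calcium.* This is an inference from the size of the limits. The documents do not say so, and the point does not need it.
- *Site 101 calcium is really in mg/dL.* Values of 8.7-10.2 taken as mmol/L would all be Grade 4 hypercalcemia. But Site 101 lists creatinine, glucose, magnesium and phosphorus in mg/dL, and sodium, potassium, chloride and bicarbonate in mmol/L. Mixed units are its pattern and are not evidence of a slip.
- *Only the grade tables are touched.* A reader might assume that observed values are safe in their recorded units. No units were recorded, so the observed-value and change summaries rest on the same assignments.

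**Conclusion.** The calcium limits at Sites 101 and 113 do not fit Appendix B, and following the SAP as written would misgrade normal values there whether the recorded analyte matches the assigned limits or is total calcium. The pooled calcium summaries are exposed as well if the assigned unit or the analyte is wrong.

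A reader might infer that all calcium grades at these sites are unusable. The documents do not support that: if the values are total calcium in a known unit, Grades 2-4 under the fixed bounds stand, and only Grades 0-1 depend on the assigned limits. The loss of low grades shown in the table needs a below-LLN rule that the SAP does not state.

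The size is 2 of the 12 sites listed in Appendix A. Enrolment by site is not given. A bound on subjects can be built by assuming that every listed site treated someone, but it is too wide to inform, and SAP 10.3 speaks of 14 centers, which Appendix A does not match. The conclusion rests on the printed limits, the numeric cut points and the unit conversion. It should be settled before the calcium tables are produced.

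**What to change.** 1. Determine from the recorded values and site information whether calcium at Sites 101 and 113 is ionized or total, and in what unit.
2. If ionized, leave it out of the albumin-corrected grading and out of the pooled total-calcium summaries. If total, assign a total-calcium range from site information or the textbook 8.7-10.2 mg/dL already used at Site 102.
3. State the albumin-correction formula for all sites. Reassigning two ranges does not close that gap.
4. State whether a hypocalcemia grade requires a value below LLN.
5. Secondary: if women were treated at Sites 104 and 113, use sex-specific hemoglobin limits from site information or a stated source.
6. Verify against the original SAP, before any correction, the Site 113 glucose unit (printed as ng/mL with limits 65-199, which fit mg/dL) and the Site 110 female creatinine ULN (printed as 882 umol/L). Either could be a reading fault in the extracted text.

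Cost: a few Appendix A rows, two added rules in the SAP, a rerun of the affected laboratory tables, and possibly queries to a few sites. No new patient assessments are needed.
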